2.3 Study design and conduct

Study ONC001 is a multicenter, nonrandomized, open-label, Phase 1/2 study evaluating the safety, PK, efficacy (as assessed by antitumor activity), PD, biomarkers, and immunogenicity (ADA activity) of intravenous (iv) UCB6114 as monotherapy and in combination with selected standard of care (SoC) regimens in study participants with advanced solid tumors.

The study has a modular design including up to 3 dose escalation modules (Parts A, B, and C), 1 dose adaptation module (Part A1), and up to 4 dose expansion modules (Parts D, E, F, and G). Depending on emerging data, not all modules may open. This SAP is focused only on the first dose escalation module of the study (Part A).

[figure not shown]
Part A consists of a Screening Period (28 days), a Treatment Period (consisting of 28-day cycles), an SFU visit (approximately 30 days after the last dose of study treatment) and a Final Visit (approximately 3 months after the last dose of study treatment). The planned duration of study treatment is 2 cycles. Participants may remain on study for additional cycles if they are receiving therapeutic benefit or until they fulfill one of the criteria for study discontinuation.

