8.2 Adverse events

The primary safety endpoints for Part A of this study are the incidence and severity of TEAEs (including SAEs) from the first dose of study treatment on Day 1 of Cycle 1 until the end of the SFU Period (up to 30 days following the last dose of study treatment), and the incidence of DLTs from the first dose of study treatment on Day 1 of Cycle 1 until the end of the DLT Observation Period (Day 28 of Cycle 1).

All AEs in Part A of the study will be coded using MedDRA® and classified as pre-treatment and treatment-emergent relative to the first dose of study treatment. Adverse events with a start date prior to the first dose of study treatment will be defined as pre-treatment AEs. A TEAE is defined as any AE with a start date on or after the first dose of study treatment up until the last dose of study treatment + 30 days. A pre-treatment AE which increases in severity on or after the first dose of study treatment will also be counted as a TEAE. Note that in this case, the pre-existing AE will have a stop date and an outcome of 'worsened' and a new AE (with the same verbatim) will be entered with the same start date and the increased severity recorded on the eCRF. Any AE (including SAEs) with an onset date later than the last dose of study treatment + 30 days will not be considered as treatment-emergent and therefore will not be included in the tabulations of TEAEs. These AEs will be considered as post-study AEs and will be listed only. Where onset dates are missing or partially missing, AEs will be assumed to be treatment-emergent, unless there is clear evidence to suggest that the AE started prior to the first dose of study treatment and it has not increased in severity. Missing or partially missing dates for AEs

will be handled as described in [Section 4.2.3](#). All AEs for a participant will be recorded in the eCRF from the time of informed consent until completion or early discontinuation of Part A of this study. Serious adverse events are to be reported up to 30 days after the Final Visit (i.e. up to 150 days after the last dose of study treatment).

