Adverse events will be assigned an NCI CTCAE severity grade (Grade 1/Grade 2/Grade 3/Grade 4/Grade 5), where possible. If a CTCAE toxicity grading is not possible, then the intensity of the AE (mild/moderate/severe) will be recorded on the eCRF. If the AE is not gradable, is serious, and is considered as life threatening, then the intensity for this AE will be missing and one of the reasons for seriousness will be recorded as life threatening.

Adverse events will also be categorized according to their relationship to study treatment (related/not related), and whether the event is a DLT, as judged by the investigator. A DLT is defined as a TEAE related to study treatment that occurs during Cycle 1 and fulfills any of the criteria listed in Section 4.1.1.4 of the protocol. The investigator is expected to record whether an AE is a DLT on the eCRF.

An overview of the number and percentage of participants who experience TEAEs will be presented. This summary will include the number and percentage of participants with any TEAEs, serious TEAEs, related TEAEs, discontinuations from study treatment due to TEAE(s), discontinuations from the study due to TEAE(s), CTCAE Grade ≥ 3 TEAEs, CTCAE Grade ≥ 3 related TEAEs, DLTs, AEs leading to death and TEAEs leading to death; event counts will also be included against each of these categories.

In addition, the following summaries will be presented by SOC, high level term (HLT) and PT:

- Incidence of TEAEs;
- Incidence of serious TEAEs;
- Incidence of non-serious TEAEs;
- Incidence of TEAEs leading to a temporary interruption and/or reduction in dose of study treatment;
- Incidence of TEAEs leading to discontinuation of study treatment;
- Incidence of TEAEs leading to discontinuation of study;
- Incidence of DLTs;
- Incidence of adverse events of special interest (AESIs) (Hy's Law – see [Section 8.2.1](#) below);
- Incidence of infusion-related reactions (defined as hypersensitivity reactions, anaphylactic reactions and cytokine release syndrome – See Section [8.2.2](#));
- Incidence of TEAEs by maximum CTCAE severity grade;
- Incidence of TEAEs by maximum relationship;
- Incidence of TEAEs by relationship;
- Incidence of serious TEAEs by relationship;

- Incidence of non-serious TEAEs by relationship;
- Incidence of fatal TEAEs by relationship;
- Incidence and event rate of TEAEs by treatment-emergent ADA positivity.

The following summaries will be presented by SOC and PT for EudraCT reporting:

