- Incidence of non-serious TEAEs above the threshold of 5% of participants in any treatment group;
- Incidence of non-serious TEAEs above the threshold of 5% of participants in any treatment group by relationship.

The above summaries of TEAEs will be ordered alphabetically by SOC, alphabetically by HLT within SOC and decreasing incidence of PT events within SOC/HLT in all study participants. For tables including only the number and percentage of participants, summaries will be ordered alphabetically by SOC, alphabetically by HLT within SOC and decreasing incidence of participants with each PT within SOC/HLT in all study participants.

The incidence of TEAEs by maximum CTCAE severity grade will be presented by CTCAE term. CTCAE term will be obtained from the NCI CTCAE Version 5.0 via a mapping of MedDRA lower level terms. This summary will be ordered by decreasing incidence of participants with each CTCAE term in all study participants.

Summary tables will contain frequency counts and percentages, and the number of events, where applicable. A study participant who experiences the same event multiple times will be counted only once in the frequency counts for the PT, but all events will be included.

In the summaries of TEAEs by relationship, participants will be counted in “Not related” and “Related” categories (or “Missing” in the case where an event has a missing relationship). A study participant who experiences the same event multiple times will be included in the most related category for the summaries by maximum relationship.

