Anti-drug (UCB6114) antibody sample status will be listed for each participant at each visit by treatment group. This listing will include sampling dates and times, the Screening assay result, the confirmatory assay result and the derived ADA sample status. In addition, the titer from the titration assay (if applicable) will be listed together with the change from Baseline in titer. The number and percentage of participants with a positive or negative sample at each visit will be summarized by treatment group. Percentages will be calculated based on the number of participants with a non-missing/sufficient sample at the visit.

Based on the ADA status of the samples, study participants will be categorized according to the following 6 ADA classifications in Table 9-3:

Table 9-3: ADA Classifications

Classification	Classification Label	Definition
1	Pre-ADA negative – treatment induced ADA negative	Includes participants who have an ADA negative status at Baseline, or missing/insufficient Baseline sample, and an ADA negative status at all sampling timepoints post-Baseline (including SFU). Participants with missing post-Baseline samples are included as long as the missing samples do not result in an unmonitored period greater than 16 weeks.
2	Pre-ADA negative – treatment induced ADA positive	Includes participants who have an ADA negative status at Baseline, or missing/insufficient Baseline sample, and an ADA positive status at any sampling timepoint post-Baseline (including SFU).
3	Pre-ADA positive – treatment reduced ADA	Includes participants who have an ADA positive status at Baseline and an ADA negative status at all sampling timepoints post-Baseline (including SFU)
4	Pre-ADA positive – treatment unaffected ADA	Includes participants who have an ADA positive status at Baseline and an ADA positive status at any sampling timepoint post-Baseline (including SFU) with titer values of the same magnitude as Baseline (≤ 1.80 -fold difference from the Baseline value) or with decreased titer values compared to Baseline (> 1.80 -fold decrease from the Baseline value).
5	Pre-ADA positive – treatment boosted ADA positive	Includes participants who have an ADA positive status at Baseline and an ADA positive status at any sampling timepoint post-Baseline (including SFU) with increased titer values compared to Baseline (> 1.80 -fold increase from the Baseline value).
6	Inconclusive	Includes participants who do not satisfy the criteria for classifications 1-5

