ADA=anti-drug (UCB6114) antibody; SFU=Safety Follow-up.

Note: The terminology 'treatment unaffected' is ambiguous as the criteria refers to ADA responses that are not increased upon dosing compared to Baseline level whereas titers may reduce.

A study participant will be classified as having **treatment-emergent ADA positivity** if they satisfy one of the following criteria:

- The Baseline result is ADA negative and at least one post-Baseline result is ADA positive (pre-ADA negative – treatment induced ADA positive) – ADA classification 2 in Table 9-3;
- The Baseline result is ADA positive and at least one post-Baseline result shows a pre-defined fold increase in titer from the Baseline value (the fold increase from Baseline required to meet this criterion will be defined with the development of the assay and will be included in the TFLs) (pre-ADA positive – treatment boosted ADA positive) – ADA classification 5 in Table 9-3.

Total anti-drug (UCB6114) antibody **incidence** will be determined by the number and percentage of participants with treatment-emergent ADA positivity (as defined above). The denominator for the percentage calculation will be the number of participants with at least one available/reported post-Baseline result.

Total **prevalence** of pre-anti-drug (UCB6114) antibody will be determined by the number and percentage of participants who are pre-ADA positive (i.e. participants who have a positive ADA status at Baseline). The denominator for the percentage calculation will be the number of participants with an available/reported Baseline sample result.

Total anti-drug (UCB6114) antibody **prevalence** will be determined by the number and percentage of participants with ADA classifications 2, 4 and 5 in Table 9-3 (i.e. an ADA positive status at any post-Baseline sampling timepoint). The denominator for the percentage calculation will be the number of participants with at least one available/reported sample result (either at Baseline and/or post-Baseline).

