The ADA classification for each participant will be listed by treatment group. This listing will also include whether or not the participant achieved treatment-emergent ADA positivity (ADA incidence), whether the participant was pre-ADA positive (pre-ADA prevalence) and whether the participant had an ADA positive status at any post-Baseline sampling timepoint (ADA prevalence). In addition, the visit at which the participant first achieved treatment-emergent ADA positivity will be included.

The number and percentage of participants in each of the 6 ADA classifications defined above in Table 9-3 will be presented by treatment group. Also, in this tabulation, ADA incidence and prevalence (as defined above) will be summarized.

The first occurrence of treatment-emergent ADA positivity (based on the criteria above) will be summarized using frequency counts and percentages at each post-Baseline visit by treatment group. This tabulation will include a count of the number of participants at each post-Baseline visit who fulfill at least one of the above defined criteria for treatment-emergent ADA positivity; participants will be counted in the numerator based on the earliest visit at which one of these criteria is fulfilled. At other visits, participants will be counted in the denominator (assuming an assessment of treatment-emergent positivity is available) and this will be used in the percentage calculations.

Individual study participant ADA titer profiles over actual time will be presented graphically on the linear and the semi-logarithmic scale. The linear scale plots will be repeated for the subset of participants who achieve treatment-emergent ADA positivity during Part A.

Mean (\pm standard deviation) C_{min} will be plotted by ADA sample status over scheduled time with treatment groups overlaid on the same plot.

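### The TEAE-by-ADA table compares ever-positive with never-positive participants, so crude incidence is expected to be higher in ADA positives even with no ADA effect, and its event rate has no stated denominator

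*SAP*

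**What the plan says.** The list of TEAE summaries in Section 8.2 of the Part A SAP includes "Incidence and event rate of TEAEs by treatment-emergent ADA positivity". The Part A1 SAP repeats the line in its own Section 8.2. Four other provisions determine what the table will contain.

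- **Grouping (Section 9.3).** A participant is treatment-emergent positive if "The Baseline result is ADA negative and at least one post-Baseline result is ADA positive", or if a positive Baseline titer is boosted by the set factor. Any post-Baseline sample can qualify, including the one at the safety follow-up (SFU) visit.
- **TEAE window (Section 8.2).** Events count from the first dose "up until the last dose of study treatment + 30 days" (Part A wording; Part A1 has the same window).
- **Counting (Section 8.2).** A participant with repeats of the same event "will be counted only once in the frequency counts for the PT, but all events will be included".
- **Length of follow-up (Section 2.3).** "The planned duration of study treatment is 2 cycles", but "Participants may remain on study for additional cycles if they are receiving therapeutic benefit".

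Section 9.3 also adds timing to the ADA classification listing: "the visit at which the participant first achieved treatment-emergent ADA positivity will be included". Nothing in Section 8.2 connects that visit to the TEAE table. Neither SAP text gives the denominator of the event rate.

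**The concern.** The label is fixed by what happens later in follow-up and is then used as if it were known at the first dose. Someone treated for many cycles gives more samples, any of which may be positive, and has more days on which a TEAE can start. Incidence, the share of participants with at least one event, rises with follow-up, so the two groups differ before ADA plays any part.

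The order of events is also lost. Section 8.2.2 defines infusion-related reactions as starting within 24 hours of the start of an infusion. Suppose a participant who is ADA negative at Baseline reacts to the first infusion and first tests positive months later. The reaction appears in the ADA-positive column although it came before any treatment-induced antibody was seen. This is the kind of event for which a reader would consult the table.

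At stake is how the clinical study report reads. Section 9.3 sends the fuller ADA-safety exploration to a separate report, so this table would appear without it.

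**Working it through.** The plan states no figure for this table, so there is none to reproduce. The check asks what the table shows when TEAEs are independent of ADA.

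**From the SAPs:** dosing every 2 weeks (Part A, and Part A1 Cohorts 1 and 2); TEAE window to last dose + 30 days; ever/never label; SFU samples count.

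**Assumed, not in the SAPs:** exponential treatment duration with median 8 or 16 weeks, capped at 365 days; ADA onset at 3% or 10% per month; ADA sampled every 14 days and at SFU; one preferred term at 0.10 events per month, with hazard constant (×1) or 3 times higher in the first 28 days (×3). Each scenario has 400,000 simulated participants.

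**Hand check, first scenario.** With constant hazard, incidence over follow-up F days is 1 − exp(−0.10 × F/30.4). At the median follow-ups of 142 days (positive) and 72 days (negative):

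- positive: 1 − exp(−0.467) = 37%
- negative: 1 − exp(−0.237) = 21%

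Averaged over the whole spread of follow-up, the simulation gives 37.6% and 25.6%.

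**Measures.** Incidence is the share with at least one event. Rate is events ÷ total follow-up, per 30.4-day month. The split rate compares time after the first positive sample with all other time. Pairs are ADA positive vs negative; for the split, after vs all other time.

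| Median weeks, ADA/month, early hazard | Incidence % | Median follow-up, days | Rate/month | Events per participant | Positives' events before first positive sample | Split rate/month |
|---|---|---|---|---|---|---|
| 8, 3%, ×1 | 37.6 vs 25.6 | 142 vs 72 | 0.100 vs 0.100 | 0.516 vs 0.321 | 54% | 0.100 vs 0.100 |
| 8, 3%, ×3 | 47.8 vs 38.2 | 128 vs 72 | 0.136 vs 0.158 | 0.700 vs 0.506 | 64% | 0.105 vs 0.158 |
| 8, 10%, ×1 | 36.0 vs 23.6 | 128 vs 72 | 0.100 vs 0.100 | 0.489 vs 0.288 | 50% | 0.100 vs 0.100 |
| 8, 10%, ×3 | 46.6 vs 36.4 | 128 vs 72 | 0.138 vs 0.164 | 0.670 vs 0.471 | 62% | 0.105 vs 0.165 |
| 16, 3%, ×1 | 51.9 vs 36.3 | 240 vs 128 | 0.100 vs 0.100 | 0.804 vs 0.514 | 50% | 0.100 vs 0.100 |
| 16, 3%, ×3 | 60.1 vs 47.0 | 240 vs 128 | 0.123 vs 0.136 | 0.991 vs 0.694 | 59% | 0.103 vs 0.136 |
| 16, 10%, ×1 | 49.7 vs 31.6 | 226 vs 100 | 0.101 vs 0.100 | 0.763 vs 0.427 | 46% | 0.101 vs 0.100 |
| 16, 10%, ×3 | 58.2 vs 43.2 | 226 vs 100 | 0.124 vs 0.143 | 0.944 vs 0.611 | 55% | 0.102 vs 0.146 |

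**Reading it.**

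1. Incidence is higher in positives in every row. The gap runs from 47.8 − 38.2 = 9.6 points to 49.7 − 31.6 = 18.1 points.
2. Events per participant are also inflated, by a factor of 0.700/0.506 = 1.4 to 0.763/0.427 = 1.8.
3. The person-time rate shows no false excess under constant hazard. With early clustering it is lower in positives.
4. Splitting time at the first positive sample is unbiased under constant hazard. With early clustering it widens the false difference (second row: 0.158 − 0.105 = 0.053, against 0.158 − 0.136 = 0.022 unsplit), because time after positivity is mostly late time.

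**The case against.** The strongest reply is that the quoted line asks for an event rate as well as incidence, and a rate per person-time removes most of the follow-up problem. That stands, on condition that person-time is what is meant. The SAPs do not say so. The table shells that might are cited in Section 1 but are not available here, and the exact column layout is also unseen.

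A reader might infer that the table manufactures a false ADA-safety link by construction, in whatever measure is used. The documents do not support that. The expected excess applies to incidence and to events per participant. A person-time rate shows none under constant hazard and the opposite sign when events cluster early. Counting pre-ADA events does not by itself create an excess in that rate, because the matching time is counted too.

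Other points that stand:

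- The table carries no test, and ADA is an exploratory endpoint.
- Safety summaries are by treatment group. In a Part A cohort of 6, a gap of 10 to 18 points is about 0.6 to 1.1 participants, so chance variation will dominate within a cohort.
- The listings give AE onset dates, ADA sample dates and the first positive visit, so the order of events can be recovered participant by participant.
- Early withdrawals are asked back for SFU, and that sample counts, so stopping early reduces the chance of a positive label without removing it.

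None of this changes what the incidence columns will show to someone who reads only the table.

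**Conclusion.** The point holds for incidence and for the undefined rate. As planned in both SAPs, crude TEAE incidence is expected to be higher in ADA-positive participants with no ADA effect, by about 10 to 18 percentage points in the scenarios run, with 46% to 64% of the events credited to them starting before the first positive sample. The direction follows from the SAPs' definitions together with unequal follow-up. The sizes are illustrative, since ADA rate, sampling schedule, treatment duration and event hazard are all assumed. For the event rate, both the size and the sign of any distortion depend on the denominator and on when events occur.

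It would go too far to infer that a dose or trial decision would be wrong. Neither SAP attaches a test or decision rule to this table. The consequence is a misleading descriptive safety table that should be corrected before reporting.

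**What to change.** In Section 8.2 of both the Part A and Part A1 SAPs:

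1. Define the event rate as number of events divided by participant-time in the TEAE window, and state the unit.
2. Within ADA-positive participants, tabulate TEAEs by onset before versus on or after the date of the first treatment-emergent positive sample. Section 9.3 already derives the visit and lists the sample dates.
3. Show the results by time since first dose, for example by cycle. A before/after split alone is confounded when TEAEs come early, as the ×3 rows show.
4. Footnote the crude incidence columns as not adjusted for length of follow-up.

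The cost is a few lines of SAP text, a date-based flag in the adverse event dataset and a revised shell. There are limits to state alongside the table:

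- Events after positivity will be few, so rates will be imprecise.
- A participant first positive at SFU, about 30 days after the last dose, has almost no later TEAE time.
- The first positive sample dates detection, not antibody onset.
- A completely missing AE onset date is imputed to the first dose (Part A Section 4.2.3, Part A1 Section 4.4.1), so such an event will always fall before ADA positivity.

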8.2.1 Adverse events of special interest

An AESI is any AE that a regulatory authority has mandated be reported on an expedited basis, regardless of the seriousness, expectedness, or relatedness of the AE to the administration of a UCB product/compound.

For ONC001, potential Hy's Law is used to identify AESIs and is defined using the laboratory data and the following potential drug-induced liver injury (PDILI) criteria:

- $\geq 3x$ upper limit of normal (ULN) alanine aminotransferase (ALT) *or* aspartate aminotransferase (AST) with coexisting $\geq 2x$ ULN total bilirubin in the absence of $\geq 2x$ ULN alkaline phosphatase (ALP), with no alternative explanation for the biochemical abnormality;
- Study participants who have evidence of liver metastases may be considered to have an alternate etiology for the described laboratory abnormalities.

All AESIs will be flagged on the listing of AEs.

